2.10 Data management

Personal data will be processed in the study, and we comply with both the Data Protection Act and the Data Protection Ordinance.

The Nellcor PM10N pulse oximeter will hold patient data for the observation time only. Following data transfer to a secure drive, all data will be cleared from the devices.

In the computer monitoring data will be stored as csv-files on a secure drive.

Patient data collected from the medical records are stored and managed using Research Electronic Data Capture (REDCap) an electronic data capture tool hosted at Rigshospitalet. This is a secure, web-based software platform designed to support data capture for research studies.²⁰

2.11 Statistics

To account for artefacts during the measurement period the method described by Haahr-Raunkjaer et al. is used. It is stated that artefacts are defined as SpO₂ values after a change in SpO₂ of more than 4% per second.²¹

Data with assumptions of normal distribution will be described with means and standard deviations, categorical data will be reported with numbers and percentages.

Data with assumption of being non-normally distributed will be reported with medians with interquartile ranges.

The student's t-test will be used for parametric data to compare the two study groups.

The Mann-Whitney-U-test will be used for non-parametric data to compare the two groups (day vs night).

A Kruskal-Wallis test will be used for non-parametric data when comparing the different hospital departments.

The modified Wald method will be used to determine the 95% confidence intervals.

A p-value of <0.05 will be considered statistically significant.

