1.2 Study objectives and hypothesis

The aim of this study is to examine the occurrence and duration of episodes of hypoxemia in trauma patients in the first 24 hours after trauma and to compare their incidences during the day (08.00-19.59) and night (20.00-07.59).

We hypothesize that hypoxemic episodes will be more frequent during the night than during the day.

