2.5 Outcomes

[figure not shown]
Primary outcome

- The occurrence and daily distribution of clinically relevant hypoxemic episodes defined as $\text{SpO}_2 < 90\%$ for > 5 minutes, within the first 24 hours after trauma

Secondary outcomes

- The occurrence of clinically relevant hypoxemic episodes $\text{SpO}_2 < 90\%$ > 5 minutes in different departments including trauma centre, ICU, general ward, operating theatre and recovery room.
- The occurrence of prolonged hypoxemic episodes $\text{SpO}_2 < 90\%$ for > 30 minutes per episode
- Cumulated time of hypoxaemia $\text{SpO}_2 < 90\%$

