2.6 Participant timeline

2.7 Sample size

We estimate that 5% of patients during the day and 20% of patients during the night will experience hypoxemia defined as $\text{SpO}_2 < 90\%$ for > 5 minutes. A sample size calculation with an alpha of 5% and a power of 80% estimates a need of 150 study participants. Based on previous experience with continuous pulse oximetry it is expected that 10% will be excluded due to unsuccessful data collection. Therefore, the aim is to include 165 patients.

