2.9 Data collection methods

Continuous pulse oximetry will be used to measure SpO_2 . SpO_2 , heart rate, pulse amplitude and alarm status will be measured every second during a 24-hour period on all study participants.

The Nellcor™ Portable SpO_2 Patient Monitoring System, PM10N (Medtronic, [name]) is used as monitoring device. The Covidien Nellcor FLEXMAX or a similar probe will be placed on the patients' index finger, alternatively another finger or toe. If there are no available extremities the patient will be excluded from the study.

If a patient has a peripheral venous catheter or a blood pressure cuff, the probe is placed on the other arm. The probe cable will be fastened with adhesive band across the back of the patient's hand, as an attempt to prevent untimely probe removal. The monitoring device will be placed in a telemetry bag with a soft fabric string which can be placed in the bed or around the patient's neck if awake. The data will be transferred and stored locally on a secure drive.

Since the study is observational, and we would like to identify episodes of hypoxemia that would go undetected under standard care, the alarm system on our monitoring device will be set restrictive. Alarm if $\text{SpO}_2 < 80\%$ or the heart rate is < 40 beats per minute or > 140 beats pr. minute.

Data collection will continue for up to 24 hours. If there is an untimely removal of the probe, the device will switch off, and data collection will stop at this point, unless the device is turned on again. After 24 hours of measurement, an investigator will collect the device and transfer the data by USB cable to a computer for secure storage and further analysis.

The following data will be obtained by accessing the study participants' medical records.

- Patient characteristics including name, unique patient identifier (civil registration number “CPR nummer”), age, sex, height and weight
- Pre-hospital circumstances including vital signs, Glasgow Coma Score (GCS), mechanism of injury, variables regarding airway management and oxygen treatment, use of sedatives and opioids, transportation mode to the trauma centre
- Vital signs at trauma centre arrival
- Clinical parameters during admission including vital signs, variables regarding airway management and oxygen treatment and use of sedatives and opioids

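### Day and night are compared with independent-sample tests, although a complete 24-hour recording supplies both periods from the same patient

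*Combined protocol and SAP*

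**What the plan says.** Section 1.2 sets the aim for hypoxemic episodes in the first 24 hours: to "compare their incidences during the day (08.00-19.59) and night (20.00-07.59"). Section 2.5 makes the primary outcome "The occurrence and daily distribution of clinically relevant hypoxemic episodes". In section 2.9, SpO2, heart rate, pulse amplitude and "alarm status will be measured every second during a 24-hour period on all study participants", although the same section allows for shorter recordings if the probe comes off and the device is not restarted.

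Section 2.7 sizes the study on patients affected, yes or no: "5% of patients during the day and 20% of patients during the night will experience hypoxemia". It then says that an "alpha of 5% and a power of 80% estimates a need of 150 study participants".

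Section 2.11 gives the tests. For non-normal data: "The Mann-Whitney-U-test will be used for non-parametric data to compare the two groups (day vs night"). For normal data, the Student's "t-test will be used for parametric data to compare the two study groups". The only interval statement is "The modified Wald method will be used to determine the 95% confidence intervals", with no quantity named. No paired test, mixed model, GEE or other allowance for repeated observation of one patient appears anywhere, and no test is named for comparing two percentages.

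**The concern.** The unpaired t-test and Mann-Whitney U take the two samples to come from different people. Here, most patients should appear in both. A patient who desaturates by day (chest injury, opioids, lung disease) is more likely than others to desaturate by night, so the two observations are probably positively correlated. An unpaired test leaves that correlation out of the standard error. Its p-value is then too large if the correlation is positive and too small if it is negative.

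This affects the study's only stated hypothesis, that episodes are more frequent at night. There are two further gaps. The endpoint used for sizing is binary, yet the listed day-night tests are for measurements or ranks. The modified Wald method gives an interval for one percentage, so the hypothesised difference has no interval at all.

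**Working it through.** **Inputs.** Day 5%, night 20%, alpha 5%, power 80%, N = 150 (section 2.7). Two-sided testing is assumed, because the plan does not say. The within-patient correlation is not given. Latent correlations of 0, 0.3, 0.5 and 0.7 are assumed, with negative values shown as a contrast.

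**1. The plan's own figure.** For two independent proportions with pooled variance and mean 0.125:

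n per group = [1.96·√(2·0.125·0.875) + 0.8416·√(0.05·0.95 + 0.20·0.80)]² / 0.15² = (0.9167 + 0.3834)² / 0.0225 = 75.1, so 76 per group and 152 in total.

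Power at 75 per group is 79.9%. The stated 150 is therefore about 2 × 75, an independent-groups figure. The sample size makes the same assumption as section 2.11.

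**2. What pairing does to the standard error.** Let b be the share of patients with a day episode only, and c the share with a night episode only. The paired variance of the difference is [b + c − (c − b)²]/n. The unpaired variance is (0.0475 + 0.16)/n = 0.2075/n. The ratio of paired to unpaired standard error at 5% versus 20% is:

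| Phi coefficient | Ratio | Unpaired SE too large by |
|---|---|---|
| 0 | 1.00 | 0% |
| 0.3 | 0.865 | 16% |
| 0.46 (maximum: every day-event patient also has a night event) | 0.784 | 28% |

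**3. Type I error.** Simulation of 150 patients, 12.5% in both periods, bivariate-normal latent variables, 20,000 replicates. The plan names no binary test, so the unpaired two-proportion z-test stands in.

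| Latent correlation | Unpaired test | McNemar |
|---|---|---|
| −0.5 | 6.2% | 4.8% |
| 0 | 4.9% | 5.0% |
| 0.3 | 3.6% | 5.6% |
| 0.5 | 2.2% | 5.2% |
| 0.7 | 1.0% | 5.1% |

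For a continuous skewed outcome (1,500 replicates), Mann-Whitney gives 8.1% at −0.3, then 5.1%, 1.5%, 0.7% and about 0% at 0, 0.3, 0.5 and 0.7. Wilcoxon signed-rank stays between 3.9% and 5.4%.

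**4. Power with 150 patients seen in both periods (simulated).**

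| Latent correlation | 5% vs 20%: unpaired / McNemar | 10% vs 20%: unpaired / McNemar |
|---|---|---|
| 0 | 98.6% / 98.6% | 69.1% / 68.8% |
| 0.3 | 98.9% / 99.3% | 69.9% / 75.4% |
| 0.5 | 99.4% / 99.8% | 71.6% / 82.5% |
| 0.7 | 99.7% / 100.0% | 74.1% / 90.4% |

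For a continuous outcome shifted by 0.25 SD, at correlation 0.5, Mann-Whitney has 58% power and signed-rank 77%.

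**5. Patients needed by a paired analysis at 5% versus 20%.** n = [1.96·√(b+c) + 0.8416·√(b+c−0.0225)]² / 0.0225. With independence within patients (b = 0.04, c = 0.19) this is 78. It is 71, 65 and 58 at latent correlation 0.3, 0.5 and 0.7. The extremes are 50 (b = 0, c = 0.15) and 85 (b = 0.05, c = 0.20).

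**The case against.** **The groups might be patients admitted by day and patients admitted by night.** They would then be independent, and the comparability check in section 3.9 leans that way. But section 1.2 compares incidences during clock periods, and section 2.7 speaks of patients experiencing hypoxemia during each. The reading does not fit the aim, and it would still leave the binary endpoint without a test.

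**The error is mostly harmless.** Under positive correlation the test is conservative and creates no excess of false positives. At the planned effect it costs almost no power, because all 150 patients contribute to both periods. Both statements stand. A reader might infer that the study is underpowered for its stated hypothesis, and the figures do not support that.

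**Not every patient supplies both periods.** This stands. Recording lasts up to 24 hours and can end when the probe is removed. A remedy that uses complete pairs only would discard some patients.

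**The intervals might be called wrong.** The documents do not support this. Modified Wald is valid for the share of patients with an episode in one period, and the plan never says that it is meant for a difference. Nor is the effect estimate invalid: with complete pairs the difference in percentages is unbiased, and only its standard error is affected.

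**Far larger power losses can be produced.** In a gamma-Poisson model of episode counts with correlations of about 0.5 to 0.8 and a 1.5-fold night rate, Mann-Whitney power is 3% to 16% against 47% to 80% for signed-rank. Those settings put 15% to 28% of patients in the day-event group, not 5%. At a fourfold rate, Mann-Whitney power in the same settings is 95% to 100%. They show what can happen with smaller effects and are no forecast for this study.

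**Conclusion.** Section 2.11 is wrong as written for the day-night comparison: independent-sample tests are applied to a contrast that lies largely within patients. No listed day-night test suits the endpoint used for sizing, and no interval is specified for the difference.

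The p-values are correct only if the within-patient correlation is zero. Over latent correlations of 0 to 0.7, the unpaired proportion test's real type I error falls from about 5% to about 1%. With negative correlation it exceeds 5%. At 5% versus 20% the power loss is about 1 point or less. At 10% versus 20% it is about 11 points at correlation 0.5 (82.5 − 71.6) and 16 points at 0.7 (90.4 − 74.1).

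These sizes rest on assumed correlations, two-sided testing and 150 patients with both periods observed. The mismatch between design and test does not depend on them.

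**What to change.** Rewrite the day-night part of section 2.11:

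- **Primary outcome (at least one qualifying episode in the period, yes/no):** McNemar's test in patients with both periods observed, reporting the paired difference with a 95% interval (for example Newcombe or Tango). State what counts as a period being observed.
- **Episode counts and cumulated time, and to keep patients with partial recordings:** a GEE or mixed model clustered on patient, with an offset for monitored time in each period. Use Wilcoxon signed-rank for complete pairs only.
- **Modified Wald:** keep it for single-period patient-level percentages, and say so.
- **Wording:** describe day and night as periods within patients. Present the section 3.9 comparability check as a separate description of patients by time of inclusion, if that is what is meant.

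The cost is somewhat more analysis work. No new data or patients are needed: 150 exceeds the 50 to 85 that a paired test requires at the planned effect. The change is best made before the data are analysed.

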2.3 Inclusion criteria

[figure not shown]
- Patients aged ≥ 18 years
- Blunt or penetrating mechanism of trauma
- Trauma team activation
- Admission to a ward/ICU from trauma centre

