- Time points including date and time of trauma, trauma centre/ICU/ward/operating theatre/recovery room arrival and departure, time and duration of anaesthesia and surgery within first 24 hours
- Injury severity score (ISS) and abbreviated injury scale (AIS) scores
- Co-morbidities prior to trauma: Categorised in heart disease, lung disease and other diseases
- Hospital and ICU LOS
- Ischaemic events (myocardial infarction or cerebral ischemia)
- Specifics of possible brain injury (type and extent) and other cerebral complications
- 30-day mortality
- Active smoker (yes/no)

Patient data will be used to describe the population of study participants. This is of great importance, to make the results transferable to the relevant trauma patients.

Time points will be used to specify study participants' location at times of desaturation.

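### The department comparison has no term for time at risk, so unequal stays are likely to produce a significant Kruskal-Wallis result even when hourly risk is the same everywhere (secondary outcome)

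*Combined protocol and SAP*

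**What the plan says.** Section 2.5 lists as its first secondary outcome the occurrence of episodes of SpO2 below 90% lasting more than 5 minutes "in different departments including trauma centre, ICU, general ward, operating theatre and recovery room". The only test that section 2.11 plans for departments is this: "A Kruskal-Wallis test will be used for non-parametric data when comparing the different hospital departments".

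Two other provisions shape the comparison. Section 2.3 requires "Admission to a ward/ICU from trauma centre", so an included patient passes through at least two of the five locations. Section 2.9 sets one recording window for all of them: "Data collection will continue for up to 24 hours".

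Section 2.9 also collects the times of "trauma centre/ICU/ward/operating theatre/recovery room arrival and departure". The only stated use of these times is to establish a participant's "location at times of desaturation". Neither 2.5 nor 2.11 defines the unit of analysis for the department comparison (patient, stay or episode), a denominator in hours, or how several stays by one patient are handled.

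**The concern.** Kruskal-Wallis compares independent groups and has no place for exposure. Both features fit this comparison badly, but with different consequences.

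- **Time at risk.** The departments divide a single window of at most 24 hours, so hours in one are hours not spent in another. A longer stay gives more opportunity for an episode. Unless stays happen to be similar, occurrence, counts and cumulated time will differ between departments even if the risk per hour does not.
- **Shared patients.** The same people appear in several groups, so the groups are not independent.

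At stake is the reading of a secondary outcome. A significant result could be taken to mean that departments differ in risk when it mainly reflects where patients spent the day.

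**Working it through.** **1. The plan's own figure.** The documents give no figure for the department comparison. The only calculation is for day versus night, in section 2.7: "We estimate that 5% of patients during the day and 20% of patients during the night will experience hypoxemia defined as" SpO2 below 90% for more than 5 minutes, and "A sample size calculation with an alpha of 5% and a power of 80% estimates a need of 150 study participants". With two-sided alpha 0.05, pooled variance and no continuity correction:

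n per group = [1.960 × √(2 × 0.125 × 0.875) + 0.842 × √(0.05 × 0.95 + 0.20 × 0.80)]² / 0.15² = 75.1, so 76 per group and 152 in total.

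With 75 per group the power is 0.799. The stated 150 is reproduced to within 2 patients, and 150 × 1.10 = 165. The 5% and 20% can therefore serve as the plan's working event rates.

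**2. Hourly rate.** If day and night are independent, the 24-hour risk is 1 − 0.95 × 0.80 = 0.24, and the rate is −ln(0.76)/24 = 0.0114 per hour. Averaging to 12.5% per 12 hours gives −ln(0.875)/12 = 0.0111, essentially the same.

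**3. What unequal time does on its own.** Take a patient with 1.5 h in the trauma centre and the remaining 22.5 h on a ward (assumed stays). At 0.0114 per hour in both places:

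- trauma centre: 1 − exp(−0.0114 × 1.5) = 1.7%
- ward: 1 − exp(−0.0114 × 22.5) = 22.6%

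That is a contrast of about 13-fold with no department effect.

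**4. Simulation with equal hourly risk in every department.** 150 patients, 24 h each, Kruskal-Wallis at 0.05, 1,000 to 2,000 runs per scenario. Because the documents give no such figures, these are assumptions: 30% go to theatre and 35% to ICU; mean stays are as in the table; the rest of the 24 h is in ICU or ward; within-patient correlation enters as a gamma frailty with variance 0, 2 or 6. The rate is constant over the 24 h. Ranges run over the three frailty settings. The outcome is the episode count.

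| Trauma centre / theatre / recovery (h) | Significant at 0.0114/h | Significant at half that rate |
|---|---|---|
| 1 / 2 / 2 | 0.999–1.00 | up to 0.99 |
| 1.5 / 3 / 3 | 0.99–1.00 | 0.87–0.96 |
| 3 / 3 / 3 | 0.90–0.995 | 0.68–0.88 |
| 4 / 4 / 4 | 0.71–0.96 | 0.51–0.73 |

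Any-episode yes/no and cumulated time gave almost the same results. A repeat simulation gave 0.74–1.00 at the protocol's rate and 0.49–0.99 at half of it.

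**5. Separating the two defects.** With equal stays in every department, the false-positive rate was 0.046 without within-patient correlation and fell to 0.016–0.030 with it (0.02–0.04 in the repeat). At 3 to 10 times the rate it was 0.000–0.017. Sharing patients therefore lowers the error rate; the inflation in step 4 comes from unequal time.

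**6. Does dividing by hours help?** Applying Kruskal-Wallis to each patient's count divided by hours still gave 0.62–1.00 at the protocol's rate. Most values are zero, and short stays produce more zeros, so the ranks still follow length of stay.

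**7. Does accounting for exposure help?** A within-patient test compared each patient's episodes with expectation in proportion to that patient's hours in each department. On the same data it gave 0.04–0.07 at the protocol's rate, 0.03–0.06 at three times that rate, and 0.04–0.10 at half, where events are sparse.

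**8. How sparse?** With mean stays of 1.5/3/3 h, and recovery used only by theatre patients not going to ICU, expected episodes are:

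- trauma centre: 150 × 1.5 × 0.0114 = 2.6
- theatre: 150 × 0.30 × 3 × 0.0114 = 1.5
- recovery: 150 × 0.30 × 0.65 × 3 × 0.0114 = 1.0

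**The case against.** The case for the plan has several parts.

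- **The tested variable is inferred.** Section 2.11 reserves Kruskal-Wallis for non-parametric data, reports categorical data as numbers and percentages, and plans modified Wald intervals. Occurrence by department could be reported descriptively without the test. This stands as a limit: the result applies if per-patient occurrence, counts or cumulated time are compared. The length of single episodes would not scale with stay in the same way. But occurrence is what section 2.5 names, and the plan leaves the unit open.
- **The stay lengths are not in the documents.** This also stands. A reader might infer from the shorter-stay scenarios that a false result is virtually certain. The documents do not support that, because the rate falls to about 0.5 when short stays lengthen to 4 h and the event rate is halved.
- **The shared patients.** A reader might infer that treating the same patients as independent groups creates the spurious effect. Step 5 shows the opposite. Nor will every patient contribute to two departments, since section 2.9 says recording stops if the probe comes off and the device is not restarted.
- **The harm is limited.** Kruskal-Wallis is an omnibus test, no pairwise department tests are planned, and describing where episodes occur is a legitimate aim. A reader might infer that the test would single out the wrong department. It names none; a misleading ranking would come from unadjusted description beside it.

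None of this supplies the missing denominator.

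**Conclusion.** The comparison is wrong as written, for a secondary outcome. If followed on per-patient occurrence, counts or cumulated time, it would probably report a department effect when hourly risk is equal: about 0.7–1.0 of the time at the protocol's event rate and about 0.5–1.0 at half that rate. These figures rest on assumed mean stays of 1–4 h in trauma centre, theatre and recovery, assumed shares going to theatre and ICU, and a constant hourly rate. The direction of the error does not depend on the exact values, provided stays are clearly unequal. Ignoring the pairing is a separate and lesser fault that costs power. The day-night primary outcome is untouched.

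**What to change.** In section 2.11, replace Kruskal-Wallis for departments with an analysis of episodes per monitored hour:

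- **Unit:** the patient-department stay, split at 08.00 and 20.00 so that day/night can be a covariate. State which department an episode belongs to if it spans a transfer.
- **Exposure:** hours of usable oximetry within each stay, from the arrival and departure times and the per-second recording.
- **Model:** Poisson or negative binomial with log(monitored hours) as offset, patient as cluster (GEE or random intercept), and adjustment for day/night. Report rate ratios with 95% CIs alongside raw counts and hours by department.
- **Sparse events:** prespecify merging of short-stay departments (for example theatre with recovery), or a within-patient conditional exact test, if events are too few for the model. Step 8 suggests that this is likely to be needed.

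Dividing counts by hours and keeping Kruskal-Wallis is not enough.

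The cost is a change of wording and slightly more analysis work, with no new data collection. The downside is wide intervals for short-stay departments, which reflects how little monitored time they contribute.
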